#### **Endoscopic activity**

- Endoscopic remission: SES-CD  $\leq 2$ .
- Endoscopic activity: SES-CD > 2 (3–6 as mildly active disease, 7–15 as moderately active disease and  $\geq 16$  as severely active disease).

#### **Observation period**

- Start of observation period – corresponds to the date of the first appointment of the study
- End observation period – 96 weeks after the basal assessment

#### **PCDAI (assessment of Crohn's Disease activity)**

The PCDAI includes:

- a) Subjective reporting of the degree of abdominal pain
- b) Presence of extraintestinal manifestations, such as fever, arthritis, rash, and uveitis
- c) Physical examination findings
- d) Weight and height
- e) Hematocrit, erythrocyte sedimentation rate, and serum albumin

The scale can be assessed at: [http://www.gedii.pt/\\_scores\\_online](http://www.gedii.pt/_scores_online)

#### **Paris classification (first episode)**

- CD: age at diagnosis, location, behavior, growth

The scale can be assessed at: [http://www.gedii.pt/\\_scores\\_online](http://www.gedii.pt/_scores_online)

### **Simple endoscopic score for Crohn's disease (SES-CD)**

The SES-CD includes four variables: ulcer size, the extent of ulcerated surface, extent of affected surface, and stenosis, from 0 to 3 in five segments of the bowel. The scale can be assessed at: [http://www.gedii.pt/\\_scores\\_online](http://www.gedii.pt/_scores_online)

## **10 STATISTICAL ANALYSIS**

### **10.1 GENERAL CONSIDERATIONS**

All quantitative variables will be summarized through descriptive statistics namely mean, median, standard deviation and range (minimum and maximum) and qualitative variables through absolute (n) and relative frequencies (%) and 95% confidence intervals (if applicable). The statistical analysis will be performed through frequency tables for qualitative variables and tables with descriptive statistics for quantitative variables.

The association between two quantitative variables will be performed through Pearson correlation coefficient or Spearman correlation coefficient, in case the normality assumption is not verified.

The association of two categorical variables will be tested through the Chi-Square test or Fisher Exact test (if applicable).

The comparison of two independent samples in respect to quantitative variables will be performed through t-test for independent samples or the Mann-Whitney non-parametric test, according to the assumption validations of the statistical test (if applicable).

The proportion of patients with clinical (PCDAI), endoscopic (SES-CD) and biomarker remission (fecal calprotectin < 200 ug/g) at each data collection time points will be summarized using 95% confidence intervals, for the overall population and for the subset of patients with active and non-active CD at study inclusion.

Results for hemoglobin, leukocytes, neutrophils, eosinophiles, basophiles, monocytes, lymphocytes, erythrocyte sedimentation rate, CRP, ferritin, iron, transferrin and fecal calprotectin (Quantum Blue), will be summarized by total number of observations (n), mean, median, standard deviation, minimum and maximum.

The correlation between fecal calprotectin levels with clinical (PCDAI) and endoscopic (SES-CD) activity of disease will be analyzed through the Pearson or Spearman (in case the normality assumption is not verified) correlation coefficient at each data collection time point:

- Fecal calprotectin levels will be correlated with PCDAI score – Day 1, week 8 and every 12 weeks up to week 96.
- Fecal calprotectin levels will be correlated with Simple endoscopic score for Crohn's disease (SES-CD) – Day 1, and Week 96.

Generalized Estimated Equations will be used to investigate clinical and endoscopic remission (homogeneity) throughout data collection time points (time-effect) for each of the two subsets (patients with severe/moderate CD; patients with mild CD at Day 1).

It is expected that: patients will achieve clinical and endoscopic remission and will maintain the remission up to week 96.

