Secondary Objective(s):	
 
•To explore the association of the fecal calprotectin assessment regarding clinical and endoscopic outcomes.
 
•To explore the association of fecal calprotectin levels with clinical outcome throughout a follow up period of 96 weeks.
 
•To explore the association of fecal calprotectin levels with endoscopic activity throughout a follow up period of 96 weeks.
 
•To evaluate the impact of azathioprine in inducing clinical remission at week 12.
 
•Among patients who achieve clinical remission with azathioprine, to evaluate the maintenance of clinical remission up to week 96.
 
•To evaluate the impact of azathioprine in inducing endoscopic remission at week 96.
 
•To evaluate the impact of azathioprine in maintaining endoscopic remission throughout a follow up period of 96 weeks.
 
•To evaluate the rate of azathioprine persistence throughout a follow up period of 96 weeks
 

	
 
•To evaluate the time until loss clinical remission
 

Study Design:	
Multicenter, prospective, observational study designed to gather and analyze data on a consecutive cohort of subjects with CD who initiated therapy with azathioprine, according to physician's clinical decision. There is no imposed experimental intervention and prescribing decisions from the study physicians will be independent of patient's participation in this study.
 
The maximum overall duration of observation for each patient is 96 weeks since the start of observation period (Day 1).

Inclusion Criteria:	
Study patients must fulfill the following criteria:
 
 
1. Male or female patients, <18 years;
 
2. Patients who are registered in the GEDII Registry;
 
3. Patients who have been treated with exclusive polymeric diet and start azathioprine at diagnosis
 
 
AND who meet one of the following:
 
 
o Moderate/Severe disease (PCDAI>31) at start of study with fecal calprotectin levels > 100 ug/g
 
o Mild disease (PCDAI>11<30) with fecal calprotectin levels > 100 ug/g and/or Endoscopic activity (Simple endoscopic score for Crohn's disease [SES-CD] ≥ 3)
 
 
 
4. Patients who gave their informed consent.
 

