Statistical methods	
The association between two quantitative variables will be performed through Pearson correlation coefficient or Spearman correlation coefficient, in case the normality assumption is not verified. The association of two categorical variables will be tested through the Chi-Square test or Fisher Exact test (if applicable).
 
The comparison of two independent samples in respect to quantitative variables will be performed through t-test for independent samples or the Mann-Whitney non-parametric test, according to the assumption validations of the statistical test (if applicable).
 
The proportion of patients with clinical (PCDAI), and endoscopic remission (SES-CD) and biomarker remission (fecal calprotectin < 200 ug/g) at each data collection time points will be summarized using 95% confidence intervals, for the overall population and for the subset of patients with active and non-active CD at study inclusion.
 
Results for hemoglobin, leukocytes, neutrophils, eosinophiles, basophiles, monocytes, lymphocytes, erythrocyte sedimentation rate, CRP, ferritin, iron, transferrin and fecal calprotectin, will be summarized by total number of observations (n), mean, median, standard deviation, minimum and maximum.
 
The correlation between fecal calprotectin levels with clinical (PCDAI score) and endoscopic (SES-CD) activity of disease will be analyzed through the Pearson or Spearman (in case the normality assumption is not verified) correlation coefficient at each data collection time point:
 
 
○ Fecal calprotectin levels will be correlated with PCDAI score – Day 1, week 8, and every 12 weeks up to week 96.
 
○ Fecal calprotectin levels will be correlated with Simple endoscopic score for Crohn's disease (SES-CD) – Day 1 and Week 96.
 
 
Generalized Estimated Equations will be used to investigate clinical and endoscopic remission (homogeneity) throughout data collection time points (time-effect) for each of the two subsets (patients with moderate/severe CD; patients with mild CD at Day 1).
 
It is expected that: patients will achieve clinical and endoscopic remission and will maintain the remission up to week 96.

Overall Study Duration:	The overall duration of the study is approximately three years (1 year of recruitment + 2-year observation period).

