## 6 STUDY POPULATION

### 6.1 INCLUSION CRITERIA

Study patients must fulfill the following criteria:

1. Male or female patients, <18 years old
2. Patients who are registered in the GEDII Registry;
3. Patients who induce remission with polymeric diet and start azathioprine at diagnosis

**AND** who meet one of the following:

- o Moderate/Severe disease (PCDAI>30) at start of study
- o Mild disease (PCDAI<30) with fecal calprotectin levels > 100 ug/g and/or Endoscopic activity (Simple endoscopic score for Crohn's disease [SES-CD] ≥ 3

4. Patients who gave their informed consent.

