## 9 ENDPOINTS

### 9.1 PRIMARY ENDPOINT

- Proportion of patients who achieve fecal calprotectin remission (< 200 ug/g) at week 12.
- Proportion of patients who maintain fecal calprotectin remission (< 200 ug/g) at week 48 and 96.
- Proportion of patients who maintain fecal calprotectin remission (< 200 ug/g) at each data collection time point up to week 96.

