### 9.3 DEFINITIONS OF INTEREST

#### **Clinical activity**

- Clinical remission among patients with CD: PCDAI<10 points during therapy with azathioprine.
- Clinically active disease among patients with CD: PCDAI points during therapy with azathioprine:
  - Mildly active disease: PCDAI >11<30
  - Moderately/severely active disease: >31

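### Remission proportions, including calprotectin remission, are planned by active versus non-active disease at inclusion, a split that is undefined and conflicts with eligibility, section 9.3 and the severity subsets used elsewhere

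*Protocol*

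**What the plan says.** Section 10.1 plans 95% confidence intervals for three kinds of remission: clinical (PCDAI), "endoscopic (SES-CD) and biomarker remission (fecal calprotectin < 200 ug/g) at each data collection time points". They are to be given "for the overall population and for the subset of patients with active and non-active CD at study inclusion". The statistical methods row of the synopsis has the same breakdown: "for the subset of patients with active and non-active CD at study inclusion". Calprotectin below 200 ug/g is the primary endpoint in section 9.1, for example "Proportion of patients who achieve fecal calprotectin remission (< 200 ug/g) at week 12", so this sentence governs how the primary endpoint is broken down.

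Later in section 10.1 the GEE for clinical and endoscopic remission is run on a different split: "for each of the two subsets (patients with severe/moderate CD; patients with mild CD at Day 1". Section 9.2 also sets the time-to-loss endpoints separately for moderate/severe and mild disease.

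The baseline categories are described in several places:

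- The synopsis admits "Moderate/Severe disease (PCDAI>31) at start of study with fecal calprotectin levels > 100 ug/g", or mild disease with PCDAI above 11 and below 30 plus raised calprotectin and/or SES-CD of at least 3.
- Section 6.1 sets moderate/severe at PCDAI above 30. For the other limb it prints "Mild disease (PCDAI<30) with fecal calprotectin levels" above 100 ug/g and/or endoscopic activity, with no lower PCDAI bound.
- Section 9.3 puts two classes under clinically active disease: "Mildly active disease: PCDAI >11<30", and moderate/severe above 31. It defines clinical remission as PCDAI below 10, and endoscopic remission separately as SES-CD of 2 or less.

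**The concern.** The breakdown assumes that some patients have non-active disease when they enter. The protocol neither defines such a group nor sets out to enrol one: a patient qualifies by having mild or moderate/severe disease, and section 9.3 calls both active. One section therefore contains two different baseline splits, and the one attached to the primary endpoint does not match the population.

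Two things are at stake. First, the analyst would have to invent a meaning for non-active, possibly after seeing the data. Second, the GEE by severity covers clinical and endoscopic remission only. With the proportions sentence using another split, no calprotectin-remission estimate is planned for mild and for moderate/severe patients, which is the breakdown that the rest of the protocol points to.

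**Working it through.** **The plan's own figure.** The only computed figure is the power statement in section 10.2: more than 95% that a one-sided 95% lower limit exceeds 0.50, with n = 80 and correlation 0.75. By Fisher's z, power = Φ((atanh 0.75 − atanh 0.50) × √(80 − 3) − 1.645) = Φ(0.4236 × 8.775 − 1.645) = Φ(2.07) = 98.1%. It reproduces, and this point does not depend on it.

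**Step 1: who can be non-active on a clinical reading?** Each PCDAI value that an eligibility text allows is classified with the section 9.3 cut-offs (remission below 10; mild above 11 and below 30; moderate/severe above 31).

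| Eligibility text | PCDAI allowed | Section 9.3 class |
|---|---|---|
| Synopsis, mild limb | above 11, below 30 | mildly active |
| Synopsis, moderate/severe limb | above 31 | moderately/severely active |
| Section 6.1, mild limb | below 10 | clinical remission |
| | 10 to 11 | no class |
| | above 11, below 30 | mildly active |
| Section 6.1, moderate/severe limb | above 30, up to 31 | no class |
| | above 31 | moderately/severely active |

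Under the synopsis, active = 80 of 80 and non-active = 0 of 80. The active column repeats the overall column, and the non-active column has no proportion and no interval.

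Under section 6.1 as printed, patients with PCDAI below 10 could enter if calprotectin exceeds 100 or SES-CD is at least 3, although the criterion labels them mild. The protocol does not say how many to expect. If this group were the non-active one, clinical remission at Day 1 would be 100% in it and 0% in the active group by construction.

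**Step 2: the endoscopic reading.** If non-active meant SES-CD of 2 or less, the group need not be empty. Mild patients can qualify on calprotectin alone, and the moderate/severe limb has no SES-CD requirement in either text. The protocol does not state this reading, and the size is again unknown.

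**Step 3: what a subset of a given size would show.** The sizes are assumptions, because the protocol gives none. The exact (Clopper-Pearson) 95% limits for x of m are the 0.025 quantile of Beta(x, m − x + 1) and the 0.975 quantile of Beta(x + 1, m − x). At an observed 50%:

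| m | x | Exact 95% interval |
|---|---|---|
| 2 | 1 | 1% to 99% |
| 4 | 2 | 7% to 93% |
| 8 | 4 | 16% to 84% |
| 16 | 8 | 25% to 75% |
| 40 | 20 | 34% to 66% |
| 80 | 40 | 39% to 61% |

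A severity stratum of 40, if the cohort happened to divide evenly, would have the m = 40 interval. The protocol does not give the actual division.

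**The case against.** The strongest reply is that an empty subset depends on one reading of an undefined term. Section 9.3 defines activity twice, clinically and endoscopically, and its clinical classes are worded as status during azathioprine therapy, not at inclusion. Section 6.1 also speaks of patients whose remission was induced by diet, and the hypothesis in section 2.5 does the same. If the PCDAI that counts is taken after diet has worked, a non-active group could be sizeable. This stands in part: a reader might infer that the analysis cannot be produced at all, or that non-active patients would be a stray few admitted by mistake, and the documents support neither. Against the diet reading, section 6.1 still requires mild or moderate/severe disease, the latter explicitly at the start of the study. The text does not settle the matter, and that is itself the defect.

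A reader might also infer damage to the primary analysis. The documents do not support that. The section 9.1 endpoints contain no subgroup, the overall proportions and intervals are unaffected, and no test or decision rests on the breakdown. Nor does the study stratify recruitment by severity: it takes one consecutive sample of 80 through two alternative eligibility limbs.

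It can be said, finally, that subgroup definitions belong in the analysis plan. That would excuse a missing detail. Here the protocol names a split that conflicts with its own eligibility text, its definitions and another analysis in the same section.

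**Conclusion.** The point holds as an undefined and inconsistent split. It has no patients on one side, and repeats the overall result on the other, when *non-active* is read by PCDAI with the synopsis limits. Under section 6.1 as printed, or on an endoscopic reading, its size is unknown; at the assumed sizes of 2 to 8 patients the interval would be close to uninformative. On any reading, the planned subgroup presentation of the primary endpoint is either uninformative or depends on a definition that the analyst must supply, and calprotectin remission by severity is not planned. The effect is confined to descriptive subgroup reporting; the overall primary estimate and the sample-size statement stand. It should be corrected, but it does not threaten the study's main result.

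**What to change.** In the statistical methods row of the synopsis and in section 10.1, replace the active/non-active phrase with mild and moderate/severe CD at Day 1, the subsets already named for the GEE.

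The change works only if those subsets have one definition. The PCDAI limits in the synopsis, section 6.1, section 9.2 and section 9.3 contradict each other: the lower bound for mild disease is present in some places and absent in section 6.1, moderate/severe starts above 30 or above 31, and scores from 10 to 11 and from 30 to 31 fall in no section 9.3 class. These passages must be reconciled so that every enrolled patient falls in exactly one stratum.

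If an activity split was really intended, define it by a stated Day 1 measure and report it in addition to the severity split.

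The cost is one phrase in two places plus the alignment of the limits in four. The change of split needs no new data, because the chronogram collects PCDAI from every patient at Day 1, and it does not alter the sample size.

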APPENDIX - Chronogram

## 1. Sinopse

Title:	Impact of AZathioprine in maintaining clinical, BIOmarkers and endoscopic remission among new pediatric patients with Crohn's disease treated with exclusive polymeric diet for induction of remission: a 2-year longitudinal analysis from the GEDII Registry – P-BIOAZA
	P-BIOAZA
Scientific Coordinator:	[name]
Disease/Condition	Crohn's disease
Rational	
Thus far, there is limited data on the impact of azathioprine in maintaining fecal calprotectin remission in CD patients.
 
Taking advantage of the valuable tool such as the GEDII Registry, the GEDII promoted a research to investigate the clinical, biomarker and endoscopic outcomes among patients with Crohn's disease and managed with azathioprine in the real-world practice. This study will follow a cohort of pediatric patients with Crohn's disease registered in the GEDII Registry who have induced remission with exclusive polymeric diet and who did initiate azathioprine at diagnosis based on physician's criteria. The cohort will be followed for a period of 2 years.
 
The primary aim of this study is to explore the potential value of azathioprine in maintaining fecal calprotectin remission in pediatric patients with CD.

Research hypothesis:	We hypothesize that pediatric Crohn's disease patients treated with exclusive polymeric diet and with azathioprine at the diagnosis will achieve and maintain fecal calprotectin remission.
Primary Objectives:	
Among patients with Crohn's disease at study inclusion, registered in the GEDII Registry:
 
 
•To evaluate the impact of azathioprine in inducing calprotectin remission (calprotectin levels < 200 ug/g) at week 12.
 
•To evaluate the impact of azathioprine in maintaining calprotectin remission (calprotectin levels < 200 ug/g) at week 48 and 96
 
•To evaluate the impact of azathioprine in maintaining calprotectin remission throughout a follow up period of 96 weeks.
 

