## 6.3 DISCONTINUATION FROM OBSERVATION PERIOD

In this study, patients will be followed up to a maximum period of 96 weeks. However, observation may be stopped prior to the 96 weeks for different reasons including, but not limited to:

- Patient discontinues the exposure of interest (azathioprine). The introduction of new treatments to CD during the follow up period will not lead to study discontinuation as long as treatment with azathioprine is not discontinued.
- Protocol violation
- Lost to follow up
- Patient withdrawal of consent
- Pregnancy
- Death

In the case observation period is stopped prior to the 96 weeks, the date of study discontinuation, the date of last intake of azathioprine and dose, and the reason for discontinuation should be recorded in the electronic CRF.

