**At week 96:**

- Colonoscopy - Simple endoscopic score for Crohn's disease (SES-CD).

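### The only repeated-measures model (GEE) is assigned to two secondary outcomes and leaves out calprotectin remission, the primary outcome measured at ten visits

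*Protocol*

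**What the plan says.** All three primary endpoints in Protocol section 9.1 concern calprotectin below 200 ug/g. The first is remission achieved at week 12. The second is "Proportion of patients who maintain fecal calprotectin remission (< 200 ug/g) at week 48 and 96". The third is "Proportion of patients who maintain fecal calprotectin remission (< 200 ug/g) at each data collection time point up to week 96". The last serves the primary objective "To evaluate the impact of azathioprine in maintaining calprotectin remission throughout a follow up period of 96 weeks".

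For this outcome, section 10.1 plans that "biomarker remission (fecal calprotectin < 200 ug/g) at each data collection time points will be summarized using 95% confidence intervals", overall and by subset. Calprotectin levels get descriptive statistics, correlations with PCDAI at Day 1, week 8 and every 12 weeks, and correlations with SES-CD at Day 1 and week 96.

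The one model for repeated data comes later in the same section: "Generalized Estimated Equations will be used to investigate clinical and endoscopic remission (homogeneity) throughout data collection time points (time-effect"), fitted in each of the two severity subsets. The statistical methods entry of the synopsis repeats this scope. The expectation that follows, that "patients will achieve clinical and endoscopic remission and will maintain the remission up to week 96", also leaves calprotectin out.

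The chronogram schedules stool sampling at ten time points, from Day 1 to week 96. SES-CD is scored at Day 1 and again only at week 96 or at discontinuation (section 7.1, under week 96: "Colonoscopy - Simple endoscopic score for Crohn's disease (SES-CD")).

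**The concern.** The method and the outcome are mismatched. The longitudinal model goes to two secondary outcomes, one of them observed on only two occasions. The primary outcome, observed on ten, is left out. Because the synopsis and section 10.1 agree, this does not look like a slip in one place.

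Two things are at stake. First, a series of visit-wise proportions gives no estimate of how the remission rate changes over follow-up with an interval that allows for the same patients being measured each time. Second, those proportions do not show whether the patients in remission at week 96 are the ones who were in remission at week 12. The word maintain in the second and third primary endpoints raises exactly that question. A calprotectin model added after the data have been seen would also be open to the charge of being post hoc.

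**Working it through.** **The plan's own figure.** Section 10.2 gives power above 95% that a one-sided 95% lower limit for a correlation exceeds 0.50 when the correlation is 0.75 and N = 80. By Fisher's z, with 0.75 taken as the true correlation: (atanh 0.75 − atanh 0.50) × √77 − 1.645 = 0.4236 × 8.775 − 1.645 = 2.07, so power is 0.981. The figure reproduces, but it concerns the correlation analysis and does not bear on maintenance of calprotectin remission.

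**Coverage by outcome.**

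| Outcome | Role | Scheduled occasions | Proportion per visit with CI | GEE |
|---|---|---|---|---|
| Calprotectin remission | primary (all three endpoints) | 10 | yes | no |
| Clinical remission (PCDAI) | secondary | 10 | yes | yes |
| Endoscopic remission (SES-CD) | secondary | 2 | yes | yes |

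**Do the visit-wise proportions determine the maintained proportion?** Assume the same remission rate p at each of the eight visits from week 12 to week 96, and an exchangeable latent-normal correlation rho within patient. Both p and rho are assumptions; the protocol gives neither. With independent visits the share in remission at all eight is p^8, for example 0.6^8 = 0.017. With correlation it is the average of Φ((t + √rho·u)/√(1 − rho))^8 over a standard normal u, where t = Φ⁻¹(p).

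| p at each visit | independent | rho 0.5 | rho 0.7 | rho 0.9 | upper bound |
|---|---|---|---|---|---|
| 0.60 | 1.7% | 18% | 28% | 42% | 60% |
| 0.70 | 5.8% | 28% | 39% | 53% | 70% |
| 0.80 | 17% | 42% | 53% | 66% | 80% |

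At 48 of 80 patients the exact 95% interval for one visit is 48% to 71%. That interval is correct for the visit but carries no information about which row entry applies.

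**Precision of a change over time (illustration).** Assume 65% in remission at week 12, 55% at week 96, 80 complete pairs and within-patient correlation phi. Write a = 0.65 × 0.35 = 0.2275 and b = 0.55 × 0.45 = 0.2475, so a + b = 0.475 and √(ab) = 0.2373.

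- Pairing ignored: 1.96 × √(0.475/80) = 0.151.
- Pairing used: 1.96 × √((a + b − 2·phi·√(ab))/80).
  - phi 0.2: 1.96 × √(0.3801/80) = 0.135
  - phi 0.4: 1.96 × √(0.2852/80) = 0.117
  - phi 0.6: 1.96 × √(0.1903/80) = 0.096

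The half-width is thus 13.5 to 9.6 points, against 15.1 if the pairing were ignored. With 60 complete pairs instead of 80 (also assumed), phi 0.4 gives 1.96 × √(0.2852/60) = 0.135, so attrition could remove much of the gain.

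**The case against.** The strongest reply is that the analysis follows the endpoints as written. They are proportions, and no primary objective or endpoint is defined as a difference between week 12 and a later week. If the third endpoint is read as being in remission at every visit, it is one yes/no value per patient, and the general rule in section 10.1 (count, percentage and, if applicable, a 95% interval) can summarise it without any model. The GEE sentence is not worded as exclusive, and an analysis plan that is not shown might extend it.

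Much of this stands. A reader might infer that the primary outcome has no valid analysis; the documents do not support that, because visit-wise proportions with proper intervals are planned. A reader might also infer that the plan would compare visits as if they were independent samples, and so waste precision. It proposes no such comparison: the independent-samples tests are described only for comparing two independent samples on quantitative variables. The 15.1-point figure is therefore a reference value, not a consequence of the plan.

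It is also fair to say that GEE alone would not settle the matter. It is population-averaged, and a flat remission rate can hide patients moving in and out of remission.

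What does not fall away is the mismatch. Section 10.1 does not leave the longitudinal analysis open: it names a method and its outcomes, in two places, and omits the primary one. The per-patient reading of the third endpoint is possible, but section 10.1 describes only the proportion at each time point.

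**Conclusion.** The point holds as a mismatch of scope. The only repeated-measures model serves two secondary outcomes and leaves out the primary outcome. The planned visit-wise proportions are valid for what they estimate, but they give neither a correlation-adjusted change over time nor the share who maintain remission throughout.

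The size can only be illustrated. A 60% rate at every visit from week 12 is compatible with roughly 2% to 42% maintained over the correlations tried, with 60% as the ceiling. The half-width for a change from 65% to 55% would be about 13.5 to 9.6 points. Both rest on assumed rates and correlations, and the second on 80 complete pairs. The study remains analysable without the change. The change is still worth making, because the method and the data are already in the plan.

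**What to change.** In section 10.1 and the synopsis:

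1. Add calprotectin remission (<200 ug/g) as a GEE outcome over weeks 12 to 96 in the overall population. Report the changes from week 12 to week 48 and from week 12 to week 96 with 95% confidence intervals.
2. Report the per-patient proportion in remission at week 12 and at every later visit up to week 96, with its 95% interval. State the denominator (all patients, or those in remission at week 12) and how missing samples count.
3. State the missing-data assumption. Section 6.3 lists "Patient discontinues the exposure of interest (azathioprine") among the reasons observation may end early, so an unweighted GEE may describe mainly the patients who stay on the drug. Add a sensitivity analysis that counts early discontinuation as not in remission.

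The cost is a few sentences, one further model and its sensitivity run, with no new visits, samples or patients. The small downside is the dependence on the missing-data assumption, which item 3 brings into the open.
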